9.2.4.2 Notes on new lesions

If a new lesion is equivocal, for example because of its small size, continued therapy and follow-up evaluation will clarify if it represents truly new disease. If repeat scans confirm there is definitely a new lesion, then progression should be declared using the date of the initial scan.

Regarding new lesions, FDG-PET imaging can complement regular scans in identifying new lesions according to the following algorithm:

1. Negative FDG-PET at baseline, with a positive FDG-PET at follow-up is a sign of progression based on a new lesion.
2. No FDG-PET at baseline and a positive FDG-PET at follow-up corresponding to a potential new site of disease must have a confirmation by anatomical assessment (e.g. CT, MRI, x-ray) as new site of disease to be considered progressive disease. In such a case, the date of progressive disease will be the date of the initial abnormal FDG-PET.

9.2.5 *Relapse/Progression, Following Surgery*

Unequivocal progression of non-measurable disease in the opinion of the treating physician (an explanation must be provided). Appearance of any new lesion/site. Death due to disease without prior documentation of progression and without symptomatic deterioration.

9.2.6 *Symptomatic Deterioration*

Global deterioration of health status requiring discontinuation of treatment without objective evidence of progression. Efforts should be made to obtain objective evidence of progression after discontinuation.

9.2.7 *Assessment inadequate, objective status unknown*

Progression or symptomatic deterioration has not been documented, and one or more target measurable lesions have not been assessed or inconsistent assessment methods were used.

9.2.8 *Objective status notes*

1. Non-measurable and non-target measurable disease do not affect Objective Status in determination of CR (must be absent; a participant who otherwise has a CR, but who has non-measurable or non-target measurable disease present or not assessed, will be classified as having a PR). However, non-measurable and non-target lesions are included in determination of progression (if new sites of disease develop or if unequivocal progression occurs in the opinion of the treating physician).

2. An objective status of PR or stable cannot follow one of CR. Stable can follow PR only in the rare case that tumor increases too little to qualify as progression, but enough that a previously documented 30% decrease no longer holds.
3. In cases for which initial flare reaction is possible (hypercalcemia, increased bone pain, erythema of skin lesions), objective status is not progression unless either symptoms persist beyond 4 weeks or there is additional evidence of progression.
4. Lesions that appear to increase in size due to presence of necrotic tissue will not be considered to have progressed.
5. For bone disease documented on bone scan only, increased uptake does not constitute unequivocal progression. However, increase in the soft tissue component of a lesion as measured by CT or MRI would constitute progression.
6. Appearance of new pleural effusions does not constitute unequivocal progression unless cytologically proven of neoplastic origin, since some effusions are a toxicity related to therapy or other medical conditions. Increase in the size of an existing effusion does not constitute unequivocal progression, since the fluid status of the participant could alter the size of the effusion.

9.3 Best Response (RECIST 1.1 criteria)

This is calculated from the sequence of objective statuses.

1. CR: Two or more objective statuses of CR a minimum of four weeks apart documented before progression or symptomatic deterioration.
2. PR: Two or more objective statuses of PR or better a minimum of four weeks apart documented before progression or symptomatic deterioration, but not qualifying as CR.
3. Unconfirmed CR: One objective status of CR documented before progression or symptomatic deterioration but not qualifying as CR or PR.
4. Unconfirmed PR: One objective status of PR documented before progression or symptomatic deterioration but not qualifying as CR, PR or unconfirmed CR.
5. Stable/no response: At least one objective status of stable/no response documented at least 6 weeks after Registration and before progression or symptomatic deterioration, but not qualifying as anything else above.
6. Increasing disease: Objective status of progression within 12 weeks of Registration, not qualifying as anything else above.
7. Symptomatic deterioration: Objective status of symptomatic deterioration within 12 weeks of Registration, not qualifying as anything else above.
8. Inadequate assessment, response unknown: Progression or symptomatic deterioration greater than 12 weeks after Registration and no other response category applies.

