Radiographic disease response assessments will occur every 6 weeks +/- 7 days (after completion of 24 weeks of study treatment, the interval can be extended to every 9 weeks +/- 7 days at the discretion of the investigator) for the duration of study participation with disposition based on the results as follows:

1. Subjects who experience disease response (CR or PR) or stable disease without evidence of clinical deterioration will continue bomedemstat and atezolizumab maintenance therapy. Absence of clinical deterioration is determined by the treating physician and is defined as follows:

- a. Absence of signs and symptoms of disease progression.
- b. Absence of rapid disease progression.
- c. Absence of progressive tumor at critical anatomical sites (e.g. cord compression) requiring urgent alternative medical intervention.

2. Subjects who experience disease progression that is isolated to the CNS are eligible to continue study treatment following definitive therapy to the CNS disease, provided that ongoing study treatment is likely to provide additional benefit to the patient, at the discretion of the investigator and after appropriate discussion with the patient. See Section 8.2.7.1 for further details.
3. Subjects who experience confirmed disease progression by RECIST 1.1 (other than isolated CNS progression) and/or clinical deterioration should discontinue study treatment (see Section 6.6.1).

Note: Subjects with unconfirmed disease progression by RECIST 1.1 who do not have evidence of clinical deterioration may continue to receive study treatment, at the discretion of the investigator and after appropriate discussion with the patient. Subjects should be monitored closely and a follow-up scan should be performed after 28 days, or sooner if clinical deterioration occurs. If the follow-up scan confirms disease progression, the subject should discontinue study treatment. See Section 8.2.7.2 for further details.

Subjects will be followed closely until disease progression per RECIST 1.1 or initiation of new anticancer treatment, whichever occurs first; and will afterwards be followed for survival until death or study termination, whichever occurs first. Blood samples for biomarker assessments will be collected at protocol-defined timepoints to support study endpoints.

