8.2.7 Radiographic Disease/Response Assessment

Radiographic assessments of measurable disease will be performed using CT imaging with IV contrast. CT scans should encompass at least the chest and abdomen. CT pelvis should be included according to usual clinical practice. RECIST 1.1 criteria will be used to assess response to therapy. Radiographic imaging will be performed every 6 weeks (42 +/- 7 days). After completion of 24 weeks of study treatment, the interval between radiographic evaluations can be extended to up to 9 weeks +/- 7 days, according to the discretion of the investigator. For patients who are known to have CNS disease at the time of enrollment, CNS imaging should be performed during study participation according to usual clinical practice.

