Correlative studies will be performed in the [name] lab at the Fred Hutchinson Cancer Center in Seattle, WA. Correlative studies will include isolation of circulating tumor cells for multi-omic analysis (e.g. measurements of DNA alterations, mRNA transcript levels, and protein abundance) and the generation of patient-derived xenograft models, to isolate circulating free DNA (cfDNA) for multidimensional analysis (e.g. DNA alterations, fragmentation patterns), and to isolate genomic DNA from peripheral blood mononuclear cells for more accurate identification of somatic mutations. The goal of correlative studies is to identify predictors of clinical benefit from bomedemstat in combination with atezolizumab.

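### Section 9.3 can refuse to count stable disease seen on a compliant early first scan, if Registration falls less than 7 days before Day 1 and scans are timed from Day 1

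*Combined protocol and SAP*

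**What the plan says.** Section 9.3 derives best response from the sequence of objective statuses. Three of its categories matter here.

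- **Item 5, stable/no response:** "At least one objective status of stable/no response documented at least 6 weeks after Registration", and ahead of any progression or symptomatic deterioration. No tolerance is given.
- **Item 6:** "Increasing disease: Objective status of progression within 12 weeks of Registration, not qualifying as anything else above".
- **Item 8:** "Inadequate assessment, response unknown: Progression or symptomatic deterioration greater than 12 weeks after Registration and no other response category applies".

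On scan timing, section 6.1 states: "Radiographic disease response assessments will occur every 6 weeks +/- 7 days". Section 8.2.7 gives the same interval as 42 ± 7 days. The interval may lengthen only after 24 weeks, so both of the first two on-treatment scans fall under the 42 ± 7 day rule.

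Two dates are left open. Registration starts the clock for best response, PFS and OS (9.3, 9.6, 9.7) but is never placed relative to Cycle 1 Day 1. The date from which the six-week scan interval is counted is not stated either.

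On use of the result, section 1.3 lists the objective response rate as an additional objective, and section 10.3 plans proportions such as response rates with confidence intervals. Section 8.2.8 adds: "The goal of correlative studies is to identify predictors of clinical benefit from bomedemstat in combination with atezolizumab".

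**The concern.** The scan schedule and the response rule use the same nominal six weeks, but only the schedule has a window. A site can follow the schedule exactly, document stable disease, and have that scan not count. The patient is then placed by whatever happens next: as increasing disease if progression comes within 12 weeks of Registration, or as response unknown if it comes later, even though both scans were adequate and on time.

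What is at stake is the descriptive best-response tabulation, any disease-control figure a reader derives from it, and any grouping of stable against progressing patients in the search for predictors of benefit. With 34 patients, moving one to three is visible. The direction is unfavourable to the treatment, because documented stability is reported as progression or as unknown.

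**Working it through.** **Inputs from the protocol.** Scan interval 42 ± 7 days (6.1, 8.2.7); stable threshold 6 weeks = 42 days and cut for items 6 and 8 12 weeks = 84 days, both from Registration (9.3); six-month PFS rates 35% and 60%, and 34 patients (10.3).

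**Assumptions.** Scans run from Day 1. Registration is g days before Day 1; g is not in the documents and is varied from 0 upward. PFS is exponential with six months = 183 days. Scan days are uniform over their windows. Nobody is in CR or PR at the first scan.

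**Step 1: the window.** 42 − 7 = 35 and 42 + 7 = 49, so there are 15 permitted days for the first scan. A stable scan on day s fails item 5 when s + g < 42.

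| g (days) | Failing first-scan days | Count of 15 |
|---|---|---|
| 0 | 35–41 | 7 |
| 1 | 35–40 | 6 |
| 3 | 35–38 | 4 |
| 6 | 35 | 1 |
| 7 or more | none | 0 |

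**Step 2: the rules applied literally, g = 0.**

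| First scan | Next event | Category under 9.3 |
|---|---|---|
| Stable, day 43 | PD, day 84 | Stable (43 ≥ 42) |
| Stable, day 38 | PD, day 80 | Increasing disease (38 < 42; 80 ≤ 84) |
| Stable, day 38 | PD, day 87 | Response unknown (38 < 42; 87 > 84) |
| Stable, day 38 | No later scan, no progression | None of the eight |

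The gaps between scans in the first three rows are 41, 42 and 49 days, all within 35–49.

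**Step 3: how many patients.** With g = 0, a patient is affected if the first scan falls on days 35–41 and progression occurs between the first and second scans. Using mid-values (first scan day 38, second scan day 38 + 42 = 80):

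share ≈ (7/15) × [S(38) − S(80)], where S(t) = exp(−λt) and λ = −ln S(183)/183.

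- 35% rate: λ = 0.005737; S(38) = 0.804; S(80) = 0.632; share = 0.467 × 0.172 = 8.0%; 34 × 0.080 = 2.7 patients.
- 60% rate: λ = 0.002791; S(38) = 0.899; S(80) = 0.800; share = 0.467 × 0.0995 = 4.6%; 34 × 0.046 = 1.6 patients.

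Summing over all permitted day pairs instead of mid-values gives the same totals. At the 35% rate the 8.0% divides into about 6.3% scored as increasing disease and 1.8% as response unknown.

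**Step 4: sensitivity to the lead.** For g = 3 the failing days are 35–38 (mid-value 36.5):

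- 35% rate: (4/15) × [S(36.5) − S(78.5)] = 0.267 × (0.811 − 0.637) = 4.6%.
- 60% rate: 0.267 × (0.903 − 0.803) = 2.7%.

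For g ≥ 7 the share is zero at either rate.

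**Step 5: sensitivity to responders.** If a fraction r of patients progression-free at the first scan are in CR or PR there, items 1–4 apply to them and carry no six-week threshold. The share is multiplied by (1 − r). As an illustration only, r = 20% turns 8.0% into 8.0 × 0.8 = 6.4%.

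**The case against.** The strongest reply is that no stated analysis uses the stable category. The response objective is the objective response rate, items 1–4 have no six-week threshold, and no disease-control rate is planned. The correlative goal speaks of clinical benefit without defining it by the 9.3 categories. This stands, and it confines the point to description.

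Second, the documents lean toward some lead between Registration and Day 1. A Patient Number is assigned at consent (8.1.7), the calendar's screening column runs from Day −28, and 6.4.2 requires one evaluation to be complete before registration. If Registration is a week or more before Day 1, the mismatch vanishes for scans timed from Day 1. This also stands, but the protocol does not settle the gap. If the interval were instead counted from a baseline scan up to 14 days before treatment, the first scan could come as early as day 35 − 14 = 21, which widens the mismatch.

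Third, item 5 could be read as a deliberate minimum duration, so that a patient stable at day 38 has simply not met it. That is a fair reading of the item alone. It does not explain why a scan the schedule accepts as the six-week assessment cannot count as one, or why a patient with two adequate scans is labelled as inadequately assessed.

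Two safeguards limit the effect. A later stable status before progression restores the category, and under 9.2.4.1 a progression call not borne out at the second assessment is recoded as pseudo-progression.

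A reader might infer that every patient with an early scan (7/15 = 47%) is misclassified. That is not so, because a patient still stable at the second scan is credited. A reader might also take the calendar's column heading, which places assessments within 7 days of Day 1 of the next cycle, to mean that all first scans fall on days 35–41. The share at g = 0 would then be 0.172, about 17%, at the 35% rate. The heading can equally mean either side of Day 1, and 6.1 and 8.2.7 give a two-sided window, so the documents do not support that figure.

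**Conclusion.** The mismatch is in the text and the literal result is wrong for some compliant patients, but it is conditional and minor. It needs scans timed from Day 1, Registration less than 7 days before Day 1, an early in-window first scan showing stable disease, and then either progression at the next scan or no later scan.

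Under exponential PFS and uniform scan windows, the share whose category changes because of progression at the next scan is at most about 8% (2.7 of 34) at the 35% rate and about 4.6% (1.6 of 34) at the 60% rate. These are ceilings under those assumptions, reached only with Registration on Day 1 and no responders at the first scan. They should not be read as expected values. Patients with no later scan are not counted in them.

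It would be tempting to conclude that the efficacy result is biased. The documents do not support that: PFS (9.6) and OS (9.7) do not use the best-response category, and the CR/PR count does not depend on item 5. Only the descriptive stable, increasing-disease and unknown categories change.

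**What to change.** In 9.3 item 5, replace the six-weeks-from-Registration condition with: *at or after the first scheduled on-treatment assessment (day 35 or later from Cycle 1 Day 1)*. All four cases in the second table then score as stable, and for scans timed from Day 1 none of the 15 permitted first-scan days fails.

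Also state the date from which the six-week scan interval runs, and how Registration relates to Cycle 1 Day 1. If the interval is to run from any date other than Day 1, the day-35 figure must be set to match.

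Leave items 6–8 as they are. Moving the 12-week cut to the end of the second scan's window (49 + 49 = day 98) is unnecessary once item 5 is aligned. If item 8 were also narrowed to patients with no adequate post-baseline assessment, a first progression documented after day 98 following missed scans would have no category; the present item 8 covers it.

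The cost is a few sentences of wording, with no extra scans or data. Making the change before analysis avoids case-by-case adjudication afterwards.

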9.4 Performance Status

Participants will be graded according to the ECOG Performance Status Scale.

POINT	DESCRIPTION
--------------	--------------------

Version 3.0 August 08, 2022

0	Fully active, able to carry on all pre-disease performance without restriction.
1	Restricted in physically strenuous activity but ambulatory and able to carry out work of a light or sedentary nature, e.g., light housework, office work.
2	Ambulatory and capable of self-care but unable to carry out any work activities; up and about more than 50% of waking hours.
3	Capable of limited self-care, confined to bed or chair more than 50% of waking hours.
4	Completely disabled; cannot carry on any self-care; totally confined to bed or chair.

9.5 Dose-limiting Toxicity (DLT) Definition

DLT to bomedemstat combined with atezolizumab is defined as the occurrence of any of the following toxicities by CTCAE 5.03 determined to be possibly, probably, or likely related to bomedemstat or atezolizumab occurring within 21 days of initiation of treatment. The specific events are:

1. Grade 4 non-hematologic toxicity (not laboratory).
2. Grade 3 non-hematologic toxicity (not laboratory) lasting >3 days despite optimal supportive care.
3. Any Grade 3 or Grade 4 non-hematologic laboratory value if:
 - a. Medical intervention is required to treat the patient, or
 - b. The abnormality leads to hospitalization
4. Thrombocytopenia leading to clinically significant sequelae (i.e., a clinically significant bleeding event or the need for prophylactic transfusions).

Note: Thrombocytopenia is defined for this purpose as a platelet count < 100x10³/mcL. A clinically significant bleeding event is defined as an event that is life-threatening, cannot be controlled, and/or results in hemodynamic instability. Prophylactic transfusion is defined as platelet transfusion in the setting of a platelet count of < 10x10³/mcL.

5. Febrile neutropenia.
6. Grade 5 toxicity.

9.6 Progression-Free Survival (PFS)

From the date of registration to the date of first document of PD or symptomatic deterioration (as defined above), or death due to any cause. PFS for participants last known to be alive without report of progression, symptomatic deterioration, or death is censored at date of last contact.

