6.6 Discontinuation of Study Treatment and/or Withdrawal from Study for Individual Subjects

Specific criteria for discontinuation of study treatment and/or withdrawal from study are listed in Sections 6.6.1 (disease progression) and 6.6.2 (other reasons).

Subjects may withdraw consent at any time for any reason or be withdrawn from the trial at the discretion of the investigator should any untoward effect occur. In addition, a subject may be withdrawn by the investigator or the Sponsor if enrollment into the trial is inappropriate, the trial plan is violated, or for administrative and/or other safety reasons.

Subjects who meet criteria to discontinue study treatment will be converted to Off Treatment status and will be followed per the Study Calendar (Section 7.0) via the End of Treatment Visit and Survival Follow-up assessments (see Section 8.5.3), including the collection of any protocol-specified blood specimens, unless consent is withdrawn, or the subject is lost to follow-up or enrolled in another clinical study.

Subjects who discontinue study treatment for a reason other than disease progression and have not initiated other anti-cancer therapy will be followed with Monitoring assessments (Section 8.5.3.3).

All subjects will be followed for survival. Subjects who decline to return to the site for evaluations will be offered follow-up by phone every 3 months as an alternative.

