8.5.3.3 Monitoring

Subjects who discontinue study treatment for a reason other than disease progression or withdrawal from study move into the monitoring phase and should be assessed radiographically every 8 weeks (56 ± 7 days) as in Section 8.2.7 to monitor disease status. Every effort will be made to collect information regarding disease status until the start of new anti-neoplastic therapy, disease progression, death, or end of the study. Information regarding post-study anti-neoplastic treatment will be collected if new treatment is initiated.

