9.7 Overall Survival (OS)

Measured from the date of registration until death from any cause. OS for participants last known to be alive is censored at the date of last contact.

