10.3 Sample Size Justification and Analysis Plans

The total accrual goal to this study is 34 eligible patients. Based on the IMPOWER133 study, we estimate that 35% of patients with ES-SCLC are alive and free from disease progression at 6 months after initiation of maintenance anti-PD(L)1 therapy. With 34 patients, this study design has 90% power to detect a 25% improvement in 6-month PFS rates (from 35 to 60%) using a 1-sided binomial test at the 5% level. The observation of 17 patients progression-free (i.e. alive without PD or symptomatic deterioration) at 6 months (a 50% rate) would be considered evidence to rule out a 35% 6-month PFS rate. With 34 patients, proportions can be estimated to within 17% with 95% confidence and any toxicity with at least 10% prevalence is likely to be observed with 97% confidence.

Additional analyses will evaluate proportions (such as toxicity or response rates within subgroups) accompanied by 95% confidence intervals. Distributions for time-to-event outcomes (PFS, OS) will be evaluated using the method of Kaplan-Meier. For point estimates at landmark times, the associated 95%

confidence interval (CI) will be calculated using Greenwood's formula and based on a log-log transformation applied on the survival function.

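### PFS is censored at last contact rather than at the last disease assessment, and Section 10.3 does not say how a patient without an assessment near 6 months is classed

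*Combined protocol and SAP*

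**What the plan says.** Section 9.6 defines PFS from registration to first documented progression, symptomatic deterioration or death, and then gives the censoring rule: "PFS for participants last known to be alive without report of progression, symptomatic deterioration, or death is censored at date of last contact". Section 9.7 uses the same date for survival: "OS for participants last known to be alive is censored at the date of last contact".

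Disease assessment and contact end at different times. Section 6.1: "Subjects will be followed closely until disease progression per RECIST 1.1 or initiation of new anticancer treatment, whichever occurs first"; survival follow-up comes after that. Section 8.5.3.3 covers patients who stop treatment without progression: "Every effort will be made to collect information regarding disease status until the start of new anti-neoplastic therapy" (or until progression, death or study end). Section 8.5.3.4 moves a patient who starts new anti-cancer therapy into survival follow-up every 12 weeks, and for that phase the Study Calendar (Section 7.0) lists survival status only. Section 6.6 adds: "Subjects who decline to return to the site for evaluations will be offered follow-up by phone every 3 months as an alternative".

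The primary decision is in Section 10.3: "The observation of 17 patients progression-free (i.e. alive without PD or symptomatic deterioration) at 6 months", out of 34, is taken as evidence against a 35% rate. That section describes Kaplan-Meier PFS and landmark estimates among the additional analyses. The only rule found for a missing scan, in Section 9.2.4.1, concerns the confirmatory scan after a single scan showing progression.

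**The concern.** A contact shows that a patient is alive. It does not show that the disease has not progressed. A patient who starts new therapy, or who is reached only by phone, goes on adding progression-free time up to the last call unless someone reports progression. In the Kaplan-Meier analysis that patient stays in the risk set as event-free, and any unreported progression pushes the curve up.

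The primary test is a separate matter. It is a count of patients and has no censoring, so Section 9.6 does not settle how an unassessed patient enters it. Section 10.3 does not settle it either: it gives no assessment window, names no deciding scan, and has no rule for a patient whose disease was not assessed around 6 months. In an open-label, single-arm trial decided by one cut-off, that classification should be fixed before the data are seen.

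**Working it through.** **Inputs.** From Section 10.3: n = 34, null rate 0.35, target rate 0.60, one-sided 5% binomial test, cut-off 17, stated power 90%. The documents do not give the number of patients without a disease assessment near 6 months, k; I assume k = 1, 2 or 3.

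**Plan's own figure.** Exact binomial:
- P(X ≥ 17 | 34, 0.60) = 0.913, which agrees with the stated 90% power.
- P(X ≥ 17 | 34, 0.35) = 0.0514. This is the k = 0 reference.

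**Kaplan-Meier landmark.** With no other censoring before 6 months, each patient with uncaptured progression who is carried past 6 months adds 1/34 = 2.9 percentage points.

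**Binomial count, unassessed patients counted as progression-free unless an event is known.** Give all 34 patients a true 6-month rate of 35%. Let d be the share of the k patients' true events by 6 months that is captured, by report or by death. Each of the k then counts as a success with probability 1 − 0.65d, and the other 34 − k with probability 0.35. The chance of a total of at least 17 is the sum over j of P(j of k count as successes) × P(X ≥ 17 − j | 34 − k, 0.35).

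| Share of events captured (d) | k = 1 | k = 2 | k = 3 |
|---|---|---|---|
| 1 (all) | 5.1% | 5.1% | 5.1% |
| 0.75 | 5.8% | 6.5% | 7.2% |
| 0.5 | 6.4% | 7.9% | 9.7% |
| 0 (no progression and no death captured) | 7.7% | 11.2% | 15.9% |

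**Binomial count, unassessed patients counted as not progression-free.** P(X ≥ 17 | 34 − k, p):

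| | k = 0 | k = 1 | k = 2 | k = 3 |
|---|---|---|---|---|
| True rate 35% | 5.1% | 3.8% | 2.7% | 1.9% |
| True rate 60% (power) | 91.3% | 87.9% | 83.5% | 78.1% |

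**Timing of scans.** On treatment, scans are due every 6 weeks, so at about weeks 6, 12, 18 and 24. The next is due between week 24 + 6 = 30 and week 24 + 9 = 33. Six months is about week 26. A patient on schedule has a scan about two weeks before the landmark, but none is scheduled at the landmark, so the plan has to name the deciding assessment.

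**The case against.** The strongest reply has four parts.

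1. **The censoring rule does not touch the primary test.** This stands. Section 9.6 governs the Kaplan-Meier analysis, and PFS as a time-to-event outcome is not a listed objective. A reader might infer that last-contact censoring inflates the count of 17 in 34; the documents do not support that. What remains for the primary test is a missing classification rule.

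2. **Section 10.3 can be read conservatively.** It speaks of observing 17 progression-free patients and calls this a 50% rate, which fixes the denominator at 34. On that reading an unobserved patient does not add to the 17. The reading is reasonable, but the text does not state it, and someone classing patients later could read it the other way.

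3. **The effect is limited by design.** This largely stands. Scans are every 6 weeks on treatment and every 8 weeks in Monitoring. Symptomatic deterioration and death are PFS events, survival is followed in all patients, progression learned from records or contact still counts, and a first progression scan without adequate follow-up is coded as progression. A reader might take 15.9% as the likely false-positive rate. It requires three unassessed patients with no progression and no death captured by 6 months, and nothing in the documents suggests that.

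4. **How to treat new anti-cancer therapy is debatable.** This stands. Censoring at new therapy and following through it are both defensible, and the absence of such censoring is not an error.

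A reader might also infer that patients who join another study leave scheduled follow-up, from the Section 6.6 wording "unless consent is withdrawn, or the subject is lost to follow-up or enrolled in another clinical study". That clause directly follows a mention of blood specimens and may qualify only those, so I do not rely on it.

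**Conclusion.** The concern holds in limited form. As written, Section 9.6 counts unassessed time as progression-free for patients still in contact after disease assessment stops. The Kaplan-Meier PFS estimate and its 6-month landmark can therefore be biased upward, to the extent that these patients have progression that is neither reported nor followed by death. The number of such patients is not in the documents and is probably small.

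For the primary test the defect is an unstated rule, not a demonstrated bias. How much the rule matters depends on the assumed k. With two unassessed patients, the chance of reaching 17 at a true 35% rate is 2.7% if they count as not progression-free. If they count as progression-free it is 6.5% with 75% of their events captured, and at most 11.2% with none captured. I am confident about the wording gap; the size rests on assumption.

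**What to change.** **Section 9.6.** Censor patients without progression, symptomatic deterioration or death at the date of the last adequate disease assessment, and keep last-contact censoring as a sensitivity analysis. State also how progression or death first reported after a long gap in assessment is handled: counting those events while censoring the other patients earlier leans the estimate downward. The two analyses together then bracket the problem.

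**Section 10.3.** Name the assessment around 6 months that decides status. State that only patients whose disease assessment then shows no progression count towards the 17, with the denominator kept at 34. Report the opposite classification as a sensitivity analysis.

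**New anti-cancer therapy.** The sponsor should state beforehand whether PFS is censored there. If so, the start date is needed. Section 8.5.3.3 promises only this: "Information regarding post-study anti-neoplastic treatment will be collected if new treatment is initiated". The case report form is not among the documents, so it may already hold the date.

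**Cost.** A few sentences, and at most one added date field; no change to visits or treatment. The estimated rate may be slightly lower. If 1, 2 or 3 patients are unassessed and count as not progression-free, power is 87.9%, 83.5% or 78.1% instead of 91.3%. The documents do not say how the 35% benchmark treated such patients, so comparability with it cannot be checked under either rule.
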